3.6 Withdrawals

Subjects may discontinue study treatment or withdraw their consent to participate in the study at any time without prejudice. The investigator may withdraw a subject from study treatment or from the study if, in his or her clinical judgment, it is in the best interest of the subject or if the subject cannot comply with the protocol.

In addition, any of the following conditions require discontinuation of the subject from study treatment:

- An adverse event or intercurrent illness that in the opinion of the investigator warrants the subject's withdrawal from study treatment;
- The investigator believes it is not in the best interest of the subject to continue on study
- Specific conditions described in the Sections 4.4 Warnings and Precautions and Guidelines for the Management of Adverse Events;
- Necessity for treatment with other anticancer treatment prohibited by protocol;
- Sexually active subjects who refuse to use medically accepted barrier methods of contraception (e.g., male condom, female condom) during the course of the study and for 4 months after discontinuation of study treatment;
- Women who become pregnant or are breastfeeding;

CONFIDENTIAL

- If the subject does not recover from his or her toxicities to tolerable Grade ≤ 2 within 6 weeks, the subject will have study treatment discontinued unless there is unequivocal evidence that the subject is benefitting. In this situation, a subject may be able to restart therapy with a dose reduction upon resolution of the toxicity and with agreement of the sponsor-investigator;
- Request by regulatory agencies for termination of treatment of an individual subject or all subjects under the protocol;
- Significant noncompliance with the protocol schedule in the opinion of the investigator;
- Progressive disease (PD) or the subject no longer experiences clinical benefit as determined by the investigator

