4.3.1 Dose Modifications, Interruptions, and Discontinuation

Subjects will be monitored for adverse events (AEs) from the time of first study intervention (i.e., biopsy, if needed, or treatment, whichever comes first) through their last follow-up visit (i.e., 30 days after the date of the last dose of study treatment). Subjects will be instructed to notify their physician immediately at the onset of any AE. Causality assessment of AEs will be determined by the investigator. AE severity will be graded by the investigator in accordance with CTCAE v.4.03.

The following should be taken into consideration in decisions regarding dose modifications (reductions or interruption):

CONFIDENTIAL

- As a general approach all AEs should be managed with supportive care at the earliest signs of toxicity considered related to the study treatment. Should this be ineffective, dose interruptions and/or reductions should be considered to prevent worsening of toxicity.
- Dose modification criteria are shown in Table 4-3.
- Dose interruptions and/or reductions should be implemented for unacceptable toxicity. Doses may be modified at any time while a subject is on treatment.
- The assigned starting dose for cabozantinib is 40 mg/day, and the assigned starting dose for erlotinib is 100 mg/day. One dose reduction level of cabozantinib and one dose reduction level of erlotinib are permitted (see Table 4-2).
- Dose reductions or interruptions may also occur in the setting of lower grade toxicity than defined in Table 4-3 if the investigator feels it is in the interest of a subject's safety and will optimize drug tolerability.
- Interruption of treatment for treatment-related AEs may occur at any time per investigator discretion. If treatment is interrupted due to related AEs for more than 6 weeks, treatment should be discontinued unless there is unequivocal evidence that the subject is benefitting. In this situation, a subject may be able to restart therapy with a dose reduction upon resolution of the toxicity per the discretion of the investigator.
- Dose interruptions for reason(s) other than related AEs (e.g., surgical procedures) can be longer than 6 weeks per the discretion of the investigator.
- Subjects may continue on only one study drug if the other drug must be stopped altogether and physician believes there is clinical benefit to staying that drug.

Guidelines for the management of specific AEs are provided in Section 4.4.1.

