4.4 Warnings and Precautions and Guidelines for the Management of Adverse Events

The most frequent adverse events experienced by \geq 20% of subjects were:

- Cabozantinib: diarrhea, fatigue, nausea, decreased appetite, vomiting, weight decreased, palmar-plantar erythrodysesthesia syndrome (PPES), constipation, hypertension, dysgeusia, dysphonia, and asthenia.
- Erlotinib: rash, diarrhea, anorexia, fatigue, dyspnea, cough, nausea, and vomiting.

Adverse events associated with laboratory abnormalities experienced by \geq 5% of subjects include:

- Cabozantinib: anemia, AST increased, ALT increased, hypothyroidism, hypokalemia, hypomagnesemia, thrombocytopenia, hypocalcemia, hypophosphatemia, lipase increased, lactate dehydrogenase (LDH) increased, neutropenia, ALP increased, hyponatremia, and leukopenia. Mild to moderate QTc interval prolongation (10-15ms) has also been observed with a QT interval calculated by the Fridericia formula (QTcF) not exceeding 500 ms.

Subjects may also experience medically important but less frequent adverse events including:

- Cabozantinib: arterial and venous thrombotic AEs (e.g., deep vein thrombosis [DVT], pulmonary embolism [PE], transient ischemic attack [TIA], and myocardial infarction

CONFIDENTIAL

[MI]), severe hemorrhagic events, proteinuria, wound healing complications, gastrointestinal [GI] perforation, abscesses including intra-abdominal and pelvic abscess, GI and non-GI fistulae formation, osteonecrosis, and reverse posterior leukoencephalopathy syndrome (RPLS).

- Erlotinib: interstitial lung disease (ILD), renal failure, hepatotoxicity with or without hepatic impairment, GI perforation, bullous and exfoliative skin disorders, MI/ischemia, cerebrovascular accident (CVA), microangiopathic hemolytic anemia with thrombocytopenia, ocular disorders, hemorrhage in patients taking warfarin, and embryo-fetal toxicity. Please refer to the package insert for more detailed information on managing these conditions.

Treatment should be permanently discontinued for the following adverse events:

- Cabozantinib: visceral perforation or fistula formation, severe hemorrhage, serious arterial thromboembolic events, nephrotic syndrome, malignant hypertension, hypertensive emergency, persistent uncontrolled hypertension despite optimal medical management, osteonecrosis of the jaw (ONJ), and serious and life-threatening RPLS.

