| ≥ 160 mm Hg (systolic) OR ≥ 110 mm Hg (diastolic) | 
 Reduce cabozantinib by one dose level^b or interrupt study treatment per investigator discretion Add new or additional anti-hypertensive medications and/or increase dose of existing medications and monitor subject closely for hypotension. If optimized antihypertensive therapy (usually to include 3 agents) does not result in BP < 150 mm Hg systolic or < 100 mm Hg diastolic, study treatment should be dose reduced further or interrupted Study treatment should be dose interrupted if upper limits of systolic BP (≥ 160 mm Hg) are sustained and not adequately manageable or if systolic BP is > 180 mm Hg or diastolic BP > 110 mm Hg, or if subject is symptomatic Re-start study treatment at the most tolerable dose and re-escalate only if BP falls to and is sustained at < 150 mm Hg systolic and < 100 mm Hg diastolic |
| Hypertensive emergency ^c | 
 Discontinue study treatment |

^a The investigator may decide to initiate or adjust antihypertensive treatment at a lower threshold than systolic BP >150 or diastolic BP >100 based on their clinical judgment and assessment of the individual subject.

^b Permitted dose levels are defined by individual protocols.

^c Hypertensive emergency is defined as uncontrolled elevated blood pressure with clinical evidence of progressive or impending end-organ damage (eg, myocardial infarction/ischemia, intracranial hemorrhage, cerebral ischemia, pulmonary edema, encephalopathy, kidney damage).

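### Section 4.4 and Table 4-6 give conflicting actions for hypertension not controlled on optimized therapy, and the table relies on a further cabozantinib reduction that may not exist

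*Combined protocol and SAP*

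**What the plan says.** **Permanent stop.** Section 4.4 introduces a list with "Treatment should be permanently discontinued for the following adverse events". Its cabozantinib entry includes "persistent uncontrolled hypertension despite optimal medical management". Section 3.6 states that "any of the following conditions require discontinuation of the subject from study treatment", and one item on its list is "Specific conditions described in the Sections 4.4 Warnings and Precautions and Guidelines for the Management of Adverse Events".

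**Graded steps.** The row of Table 4-6 for systolic pressure of at least 160 or diastolic pressure of at least 110 mm Hg gives these instructions in order:

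- "Reduce cabozantinib by one dose level" or interrupt study treatment, at the investigator's discretion.
- Add or increase antihypertensive drugs.
- If optimized therapy (usually three agents) does not bring pressure below 150 systolic or 100 diastolic, "study treatment should be dose reduced further or interrupted".
- Interrupt if systolic pressure stays at 160 or more and cannot be adequately managed, or "if systolic BP is > 180 mm Hg or diastolic BP > 110 mm Hg", or if there are symptoms.
- Restart at the dose best tolerated, with re-escalation tied to sustained control.

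The table's only discontinuation row is for hypertensive emergency. The text of Section 4.4.1.7 adds hypertensive crises and encephalopathy.

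**Dose levels.** Section 4.3.1 says "One dose reduction level of cabozantinib and one dose reduction level of erlotinib are permitted". Table 4-2 takes cabozantinib from 40 mg to 20 mg and calls for discontinuation if 20 mg is not tolerated. Section 4.3.2 allows a restart at the lowest dose if judged safe, and discontinuation if that dose cannot be tolerated. Footnote b to Table 4-6 leaves the permitted levels to individual protocols and does not point to Table 4-2.

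**The concern.** Three features of the hypertension rules do not fit together.

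- Blood pressure that stays high despite optimized treatment is a permanent stop in one place. In another it is a reason to reduce or interrupt, with a route back onto treatment.
- The table calls for a second downward step in a protocol that has one.
- Within one table row, two diastolic triggers cover almost the same values but give different latitude.

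Section 4.4.1.7 itself describes hypertension as a common class effect, so these rules may well be needed. At stake is whether a given patient continues cabozantinib. Safety and tolerability is a secondary objective. If stopping depends on which section the investigator consulted, the record of who stopped for toxicity partly reflects the wording of the protocol and not only the tolerability of the regimen.

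**Working it through.** The plan states no figure on this point, so the check compares the sections, counts dose levels and compares thresholds.

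**1. Action for each blood pressure state**

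| State | Sections 4.4 and 3.6 | Section 4.4.1.7 and Table 4-6 |
|---|---|---|
| Optimized therapy has failed, pressure at or above 160/110 at row entry | Permanent stop, if the state counts as persistent | Reduce further or interrupt |
| Systolic pressure stays at 160 or more and is not manageable | Permanent stop, if the state counts as persistent | Interrupt, restart foreseen |
| Hypertensive emergency | Permanent stop | Discontinue |

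The columns agree only in the last row. In the first two, everything depends on when uncontrolled hypertension becomes persistent. No section defines this, and none says that Section 4.4 takes over after the table's steps have been tried. Section 4.4 says treatment should be stopped; the mandatory wording comes from Section 3.6.

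**2. Dose levels available for cabozantinib**

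- Inputs: starting dose 40 mg; permitted reductions 1 (Section 4.3.1); reduced dose 20 mg (Table 4-2).
- If the row's first instruction is carried out as a reduction, levels remaining = 1 − 1 = 0. The later instruction to reduce further then has no cabozantinib dose to go to, and only interruption is left.
- If the first instruction is carried out as an interruption without a reduction, levels remaining = 1 − 0 = 1, and the later reduction can be made.
- A patient already at 20 mg because of another toxicity enters the row with 0 levels remaining.

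Footnote b does not settle this. It defers to individual protocols, and this document is the protocol.

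**3. Diastolic triggers in the same row**

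- Reduce or interrupt at discretion: diastolic ≥ 110 mm Hg.
- Interrupt: diastolic > 110 mm Hg.
- Values where reducing without interrupting remains open on the diastolic criterion: those that are ≥ 110 but not > 110, which is 110 exactly.

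On the systolic criterion the discretionary range is real. It opens at 160, and the automatic interruption threshold is above 180, apart from pressure that is sustained and unmanageable or patients with symptoms.

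**The case against.** The strongest reply is that the rules are sequential: Table 4-6 gives the steps, and Section 4.4 names the end state. The table's blood pressure rows sit under a subheading for patients not yet on optimized antihypertensive therapy. Other sections offer routes to a stop: Table 4-2 and Section 4.3.2 when 20 mg is not tolerated, and Section 4.3.1 when a treatment-related interruption exceeds 6 weeks without unequivocal benefit. This reading is workable, but the protocol does not state it. Despite the subheading, the row goes on to cover failure of optimized therapy, and it answers pressure that stays high and unmanageable with interruption and a restart provision. The 6-week rule has a benefit exception that the Section 4.4 list lacks.

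Three narrower replies do stand, and they limit the point:

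- A reader might infer that a patient at 20 mg is left with no action. That is not so: each relevant instruction also offers interruption. The instruction to reduce further could in principle take in erlotinib's own single level, although the table concerns hypertension related to cabozantinib.
- A reader might infer that the diastolic rules are incompatible. They overlap, but an investigator who interrupts above 110 satisfies both.
- Investigator discretion is built in throughout Section 4.3.1, so some variation between investigators is intended. That does not extend to discontinuations that Section 3.6 makes mandatory.

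**Conclusion.** The conflict is real and should be corrected. As written, persistent hypertension on optimized therapy, short of a hypertensive emergency, crisis or encephalopathy, can lead either to a required permanent stop or to reduction or interruption with a possible restart. The transition between the two is not stated. In addition, the further reduction cannot be carried out for cabozantinib once its one level is used, and the diastolic thresholds overlap.

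The size cannot be given as a patient count. It is tempting to take the list in Section 4.4 of events seen in at least 20% of subjects, which includes hypertension for cabozantinib, and compute 0.20 × 37 = 7.4 patients. That figure counts any hypertension. It does not count hypertension refractory to optimized therapy, for which the documents give no rate, and 37 patients are treated only if the second stage is reached. Section 5.2 also excludes hypertension uncontrolled at entry.

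Nor do the documents support calling the safety data uninterpretable. Section 8.3 does not define time on treatment as an endpoint, and the adverse event incidence summaries in Section 8.8 can still be produced. The supportable consequence is inconsistent decisions to stop treatment, and so an inconsistent record of discontinuation for toxicity. The two-stage response rule (0 of 11, then 2 or fewer of 37) is unaffected.

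The conclusion rests on the current text alone and takes no view on which clinical rule is right.

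**What to change.** The sponsor should reconcile Section 3.6, Section 4.3.1 with Table 4-2, Section 4.3.2, Section 4.4, and Section 4.4.1.7 with Table 4-6, so that one action follows from each blood pressure state. The amended text should:

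- state when the table's steps end and the Section 4.4 discontinuation applies, including what makes uncontrolled hypertension persistent;
- refer only to dose levels that exist in Table 4-2, and replace footnote b with a reference to that table;
- set diastolic thresholds that do not overlap.

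Which action belongs to which state is a clinical decision for the sponsor.

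The cost is amendment wording, with the approvals that Section 11.3 requires. Sample size, the two-stage rule and the planned analyses do not change.

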4.4.1.8 Thromboembolic Events

Thromboembolic complications are frequent in cancer patients due to procoagulant changes induced by the malignancy or anticancer therapy including inhibitors of VEGF pathways. Deep vein thrombosis and PE have been observed in clinical studies with cabozantinib; including fatal

CONFIDENTIAL

events (please refer to the Investigator's Brochure). Subjects who develop a PE or DVT should have treatment held until therapeutic anticoagulation with heparins (e.g., low molecular weight heparin [LMWH]) is established. LMWH are the preferred management for thrombotic events, warfarin is not recommended although is allowed at investigator discretion. Treatment may be resumed in subjects who are stable and have uncomplicated PE or DVT and are deriving clinical benefit from treatment and that anticoagulation does not place them at a significant risk that outweighs the benefit of resuming treatment per discretion of the investigator/PI. During anticoagulation treatment, subjects need to be monitored on an ongoing basis for bleeding risk and signs of bleeding which may require additional or more frequent laboratory tests in accordance to institutional guidelines. If there are any signs of clinically significant bleedings, treatment should be permanently discontinued.

Arterial thrombotic events have been observed in studies with cabozantinib (e.g., transient ischemic attack, myocardial infarction) and erlotinib (e.g., myocardial infarction/ischemia, cerebrovascular accident). Treatment should be discontinued in subjects who develop an acute myocardial infarction, cerebral infarction or any other clinically relevant arterial thromboembolic complication.

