4.4.1.13 Hemorrhagic Events

Hemorrhagic events have been reported with cabozantinib. In order to mitigate risk of severe hemorrhage, subjects should be evaluated for potential bleeding risk factors before initiating treatment and monitored for bleeding events with serial complete blood counts and physical examination while on study. Risk factors for hemorrhagic events may include (but may not be limited to) the following:

CONFIDENTIAL

- Tumor of the lung with cavitory lesions or tumor lesions which invades, encases, major blood vessels. The anatomic location and characteristics of tumor as well as the medical history must be carefully reviewed in the selection of subjects for treatment;
- Recent or concurrent radiation to the thoracic cavity;
- Active peptic ulcer disease, inflammatory GI diseases including Crohn's disease and ulcerative colitis;
- Underlying medical conditions which affect normal hemostasis (e.g., deficiencies in clotting factors and/or platelet function, or thrombocytopenia);
- Concomitant medication with anticoagulants or other drugs which affect normal hemostasis;
- History of clinically significant hemoptysis.

Treatment should be discontinued in subjects with serious and life-threatening bleeding events or recent hemoptysis (≥ 2.5 mL of red blood).

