4.5.3 Allowed Therapies

- Antiemetics and antidiarrheal medications are allowed prophylactically in accordance to standard clinical practice if clinically indicated;
- Granulocyte colony-stimulating factors (G-CSF or GM-CSF) are allowed if used per clinical guidelines (e.g., American Society of Clinical Oncology [ASCO] or [European Society for Medical Oncology] ESMO guidelines);
- Drugs used to control bone loss (e.g., bisphosphonates and denosumab) are allowed if started before screening activities but may not be initiated or exchanged during the course of the study and require PI approval;
- Transfusions, hormone replacement, and short term higher doses of corticosteroids should be utilized as indicated by standard clinical practice;
- Individualized anticoagulation therapy with heparin is allowed if it can be provided safely and effectively under the following circumstances:
 - *Low dose heparins for prophylactic use* are allowed if clinically indicated and the benefit outweighs the risk per the investigator's discretion.
 - *Therapeutic doses of low molecular weight heparins (LMWH) at the time of first dose* are allowed if the subject has been on a stable dose of LMWH for at least 6 weeks, and has had no clinically significant hemorrhagic complications from the anticoagulation regimen or the tumor.
 - *Therapeutic doses of low molecular weight heparins (LMWH) after first dose* are allowed if clinically indicated (e.g., for the treatment of deep venous thrombosis), and the benefit outweighs the risk per the investigator's discretion. For

CONFIDENTIAL

management of thromboembolic complications while on study, refer to Section 4.4.1.8.

- Accepted clinical guidelines regarding appropriate management while receiving anticoagulation therapy with heparins must be followed. This includes, but is not limited to, subject education regarding potential adverse drug reactions, monitoring laboratory parameters, dose adjustments (e.g., due to kidney dysfunction);
- For restrictions on oral anticoagulants see Section 4.5.4.

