4.5.4 Prohibited or Restricted Therapies

The following therapies are prohibited while the subject is on study:

- Any investigational agent or investigational medical device;
- Therapeutic doses of oral anticoagulants (e.g., warfarin or other coumarin-related agents, direct thrombin or direct FXa inhibitors, or antiplatelet agents such as clopidogrel, or chronic use of aspirin above low dose levels for cardioprotection per local applicable guidelines);
- Any other systemic anticancer treatment (e.g., chemotherapy, immunotherapy, radionuclides) and local anticancer treatment such as surgery, ablation, or embolization.

The following therapies should be avoided if possible, while the subject is on study:

- Palliative external radiation to bone metastasis for bone pain should not be performed while on study. Subjects who have such an intervention may be considered not evaluable (and may be assigned a censoring or progression date) for certain efficacy endpoints;

CONFIDENTIAL

- Erythropoietic stimulating agents (e.g., epoetin alfa and darbepoetin alfa) should not be used based on a report of increased risk of tumor recurrence and/or progression associated with erythropoietin;¹³
- Chronic co-administration of cabozantinib with strong inducers of the CYP3A4 family (e.g., phenytoin, carbamazepine, rifampin, rifabutin, rifapentine, phenobarbital, and St. John's Wort) may significantly decrease cabozantinib and erlotinib concentrations and should be avoided. Selection of alternate concomitant medications with no or minimal CYP3A4 enzyme induction potential is recommended;
- Caution must be used when discontinuing treatment with a strong CYP3A4 inducer in a subject who has been concurrently receiving a stable dose of cabozantinib or erlotinib because this could significantly increase the exposure to cabozantinib and erlotinib;
- Co-administration of cabozantinib with strong inhibitors of the CYP3A4 family (e.g., ketoconazole, itraconazole, clarithromycin, indinavir, nefazodone, nelfinavir, and ritonavir) may increase cabozantinib and erlotinib concentrations and should be avoided. Grapefruit and Seville oranges may also increase plasma concentrations of cabozantinib and erlotinib and should be avoided.

Additional information on potential drug interactions with cabozantinib and erlotinib is provided in Section 4.5.5.

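### Section 4.4.1.8 lets the investigator use warfarin for an on-study thrombosis, section 4.5.4 prohibits therapeutic warfarin on study, and nothing says which rule prevails

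*Combined protocol and SAP*

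**What the plan says.** Three sections of the protocol govern anticoagulation during treatment.

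- **Section 4.4.1.8 (Thromboembolic Events)** holds study treatment after a pulmonary embolism (PE) or deep vein thrombosis (DVT) until therapeutic anticoagulation with heparins is in place. It prefers low molecular weight heparin (LMWH) and then states that "warfarin is not recommended although is allowed at investigator discretion". Study treatment may restart in stable patients with an uncomplicated event who are benefiting, if the anticoagulation risk is judged acceptable.
- **Section 4.5.4 (Prohibited or Restricted Therapies)** opens with "The following therapies are prohibited while the subject is on study". One of the entries under that line is "Therapeutic doses of oral anticoagulants (e.g., warfarin or other coumarin-related agents, direct thrombin or direct FXa inhibitors". A second, softer list in the same section covers therapies to be avoided where possible. Warfarin is not on it.
- **Section 4.5.3 (Allowed Therapies)** gives a permission limited to heparin: "Individualized anticoagulation therapy with heparin is allowed if it can be provided safely and effectively". It points to section 4.4.1.8 for "management of thromboembolic complications while on study, refer to Section 4.4.1.8", and a separate bullet reads "For restrictions on oral anticoagulants see Section 4.5.4".

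Exclusion criterion 7 in section 5.2 bars therapeutic oral anticoagulation at entry. It does not address a clot that arises on study.

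**The concern.** An investigator treating an on-study DVT or PE finds warfarin permitted in one operative section and banned in another. A patient given therapeutic warfarin in line with section 4.4.1.8 thereby breaches section 4.5.4.

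The protocol itself supplies the reason to care. Section 4.4 lists "hemorrhage in patients taking warfarin" among the medically important erlotinib events and severe hemorrhage among those for cabozantinib. Section 4.4.1.13 names as a bleeding risk factor "Concomitant medication with anticoagulants or other drugs which affect normal hemostasis". Section 4.4.1.8 describes thromboembolic complications as frequent in cancer patients, so the situation is foreseeable.

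Conduct is also at stake. Deviations must be entered in OnCore within 5 days (section 9.7), and violations must be reported to the IRB (section 11.2). The same prescription could be recorded as permitted care in one patient and as a deviation in another.

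**Working it through.** The plan states no figure on this point, so the check is a comparison of the texts, followed by a conditional illustration of frequency.

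**The two rules compared**

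| | Section 4.4.1.8 | Section 4.5.4 |
|---|---|---|
| Situation | PE or DVT during treatment | Whole time on study |
| Warfarin | Discouraged, but left to the investigator | Prohibited at therapeutic doses |
| Exception or cross-reference | None to 4.5.4 | None for thrombosis, none to 4.4.1.8 |

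**Readings that might reconcile them**

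1. *Warfarin only below therapeutic doses.* This fails. Section 4.4.1.8 concerns treatment of an established clot and speaks of therapeutic anticoagulation, which is the dosing that section 4.5.4 bans for oral agents.
2. *Warfarin only while study drug is held.* This fails. The ban runs for the time on study, not the time on drug, and section 4.4.1.8 allows study treatment to resume during anticoagulation.
3. *The specific rule overrides the general one.* This is possible, but the protocol does not say so. The opposite reading is equally available, because section 4.5.3 names section 4.5.4 as the place for restrictions on oral anticoagulants.
4. *The entry rule settles it.* It does not. Exclusion 7 applies before the first dose.

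The conflict is confined to oral agents. A patient treated with LMWH breaches neither section.

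**How often it could arise (illustration only)**

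The documents give neither the on-study venous event rate, *v*, nor the share of events treated with warfarin, *w*. Assume *v* from 5% to 20% and *w* from 10% to 25%. The per-patient probability is p = v × w, the expected count is n × p, and the chance of at least one case is 1 − (1 − p)^n. Section 8.5 gives n = 40 as the maximum enrolment and n = 11 as the first stage.

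| n | v | w | p | Expected patients | Chance of at least one |
|---|---|---|---|---|---|
| 40 | 0.05 | 0.10 | 0.005 | 0.20 | 1 − 0.995^40 = 18% |
| 40 | 0.20 | 0.25 | 0.050 | 2.00 | 1 − 0.950^40 = 87% |
| 11 | 0.05 | 0.10 | 0.005 | 0.06 | 1 − 0.995^11 = 5% |
| 11 | 0.20 | 0.25 | 0.050 | 0.55 | 1 − 0.950^11 = 43% |

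The n = 11 rows matter because section 8.5 gives a 0.757 probability of stopping after the first stage if the combination is inactive. The rows pair low with low and high with high, so they mark the extremes of the assumed ranges.

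**The case against.** The strongest reply accepts the contradiction and disputes its weight.

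- **Safeguards apply either way.** Treatment is held until heparin anticoagulation is established, and resumption needs a risk-benefit judgement. Bleeding monitoring is required during anticoagulation, and clinically significant bleeding ends treatment permanently. PT/INR is scheduled at Cycle 1 Day 15, Cycle 2 Days 1 and 15, and every 4 weeks from Cycle 3. *This stands*: the safeguards reduce the likely harm. They do not tell the investigator whether warfarin may be used.
- **The setting is small.** Section 3.5 names one institution, and section 9 requires weekly review meetings that include the principal investigator. Inconsistent handling is less likely than in a large multicentre trial. *This stands* as a reason for lower practical risk, though section 7.2.4 also refers to participating sites.
- **An effect on the efficacy analysis is speculative.** Section 8.4.3 removes patients with significant protocol violations, but section 8.7 gives eligibility and treatment plan as its examples and does not name concomitant medication. *This stands*: removal is possible but not established.
- **The frequency figures rest on assumed inputs.** *This stands*: they show scale and do not support the severity of the point.
- **Deleting the permission is partly a clinical decision.** Heparins would then be the only anticoagulants that the protocol expressly allows, and a patient who cannot take heparin would lose the discretionary option. *This stands* as an inference from the text, since the documents do not discuss such patients. It is a reason to offer a second form of the fix.

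**Conclusion.** The concern holds. Sections 4.4.1.8 and 4.5.4 give opposite instructions on therapeutic warfarin for an on-study clot, and no section resolves them. This is an internal inconsistency in a safety rule that should be fixed. The hypothesis, stopping rule, sample size and endpoint definitions are unaffected.

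The size in patients is unknown. Under the assumed ranges it is 0.2 to 2.0 of 40 patients, and fewer if the trial stops at 11. The conclusion does not rest on those assumptions; it follows from the wording of the two sections.

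**What to change.** Preferred: delete the second half of the warfarin statement in section 4.4.1.8, the part that grants investigator discretion. The section then agrees with the heparin-only permission in section 4.5.3 and the prohibition in section 4.5.4.

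Alternative, if the sponsor wants an oral option, for example for patients who cannot take heparin: add to section 4.5.4 an explicit exception for warfarin started for an on-study thrombosis under section 4.4.1.8. State there that such use is not a significant protocol violation for sections 8.4.3 and 8.7.

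Exclusion 7 needs no change. The drafting cost is one clause removed or one exception added. The first form also gives up a treatment option, so the sponsor should choose between the two on clinical grounds.
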